Procedures for Assessing Efficacy Parameters

The procedures are questionnaire based apart from the Actigraphy. This consist of a band worn around the wrist.

9. Assessment of Safety

Specification, Timing and Recording of Safety Parameters.

Sleep Deprivation has no reported side effects apart from tiredness. For light therapy, a few people may experience nausea or headache after beginning treatment. (In healthy individuals bright light therapy was not associated with any significant difference in side effects compared to dim light therapy (Botanov, 2013). However, patients with any significant side effects may be asked to reduce the exposure time by 10 minutes. Triple Chronotherapy may theoretically trigger a manic episode, but patients with bipolar disorder are excluded and so this should be rare. We will however warn the patient and carer of this rare possibility.

Procedures for Recording and Reporting Adverse Events

Adverse Event (AE): Any untoward medical occurrence in a subject to whom a therapy has been administered including occurrences which are not necessarily caused by or related to that therapy.

Adverse Reaction (AR): Any untoward and unintended response in a subject to a therapy which is related to any duration of therapy administered to that subject.

Unexpected Adverse Reaction (UAR): An adverse reaction the nature and severity of which is not consistent with the information known about the therapy in question in the view of the investigator

Serious adverse Event (SAE), Serious Adverse Reaction (SAR) or Unexpected Serious Adverse Reaction (USAR): Any adverse event, adverse reaction or unexpected adverse reaction, respectively, that

- Results in death;
- Is life-threatening;
- Required hospitalisation or prolongation of existing hospitalisation;
- Results in persistent or significant disability or incapacity;
- Consists of a congenital anomaly or birth defect.

Reporting Responsibilities

All SARs and SUSARs (excepting those specified in this protocol as not requiring reporting) will be reported immediately by the Chief Investigator to the REC and Sponsor.

9.1.1 *Adverse events that do not require reporting*

Symptoms such as tiredness, nausea, headache as described above do not require reporting. An episode of mania may be regarded as Adverse Reaction.

Stopping Rules

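### The exemption of tiredness, nausea and headache from reporting is not limited to non-serious cases, so a serious reaction of these types could go without immediate notice to the REC and sponsor

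*Combined protocol and SAP*

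**What the plan says.** Section 9 of the protocol defines adverse events and reactions, and then the serious forms of each by a list of outcomes. One of these is "Required hospitalisation or prolongation of existing hospitalisation". An unexpected reaction is "An adverse reaction the nature and severity of which is not consistent with the information known about the therapy in question".

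Under Reporting Responsibilities there is a single duty: "All SARs and SUSARs (excepting those specified in this protocol as not requiring reporting) will be reported immediately by the Chief Investigator", with the REC and the sponsor as recipients.

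Section 9.1.1 follows directly, headed "Adverse events that do not require reporting". Its exempting sentence is "Symptoms such as tiredness, nausea, headache as described above do not require reporting". The back-reference leads to the start of section 9: "Sleep Deprivation has no reported side effects apart from tiredness", and "For light therapy, a few people may experience nausea or headache after beginning treatment".

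Sections 11 and 12 state that there is no steering committee and no data monitoring committee.

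**The concern.** An exemption for expected, minor symptoms is ordinary and sensible. This one is attached to the sentence on serious reactions, and nothing in it stops it from covering a serious case. An investigator who follows the text could treat a hospitalised headache as exempt because of its type, although its outcome makes it serious.

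What is at stake is the speed at which the REC and the sponsor learn of a serious reaction to the tested intervention. The Stopping Rules allow the sponsor or the Chief Investigator to end the trial on new safety information. Without an independent committee, immediate reporting is the only prompt way for that information to leave the study team.

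**Working it through.** No arithmetic applies. The check sets the relevant sentences side by side.

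1. **What must be reported.** The duty covers SARs and SUSARs only. (The definitions use a slightly different abbreviation for the unexpected serious form; I take the two to mean the same.) No sentence in section 9 or elsewhere requires a non-serious adverse event to be reported to the REC or sponsor.

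2. **What is excepted.** The parenthesis removes from this duty whatever the protocol specifies as not needing a report. The only such specification is the symptom sentence in 9.1.1. The next sentence there says that mania may be classed as an adverse reaction; it exempts nothing.

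3. **What the exception can act on.** By step 1, non-serious events are outside the duty already, so exempting them changes nothing. If the parenthesis has any effect, that effect falls on reactions already classed as serious. It covers SUSARs as well as SARs, although the definition of an unexpected reaction depends on its nature and severity.

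4. **Whether 9.1.1 limits itself.** Its heading speaks of adverse events in general. Its sentence gives no grade and no seriousness limit. The text it refers back to names tiredness, nausea and headache, also without grade or seriousness. The words *such as* mean that the three symptoms are examples and not a closed list.

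5. **Whether an exempt symptom can be serious.** Yes, under the protocol's own criteria. A headache judged related to the intervention that leads to admission meets the hospitalisation criterion. It is then a serious adverse reaction under the definitions and an exempt symptom under the literal text of 9.1.1.

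6. **Whether another passage closes the gap.** Section 4 says that the frequency of side effects is monitored in both groups. The table in section 8 lists reported side effects among the measures compared between groups; the item label says 1 week, while its timepoint column runs through all follow-up visits to 6 months. These provide for collection. Neither creates a duty to notify the REC or sponsor of a serious case. Section 14 requires compliance with GCP and applicable regulations, but in general terms that do not narrow the exemption.

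**The case against.** The best case for the plan rests on the back-reference in 9.1.1. The symptoms described earlier are plainly the expected, minor kind: tiredness after a night awake, and nausea or headache in a few people starting light therapy. A headache that puts someone in hospital is arguably not the headache described there. On that reading, with the GCP clause behind it, a careful investigator would report the serious case. This stands in part. It is why the conclusion is that such a case *could* go without immediate reporting, and not that it *would*. It does not remove the defect, because the passage referred to states no severity limit and, on this reading, the exception has nothing to act on.

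A reader might infer several stronger points that the documents do not support:

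- **That such reactions would go unrecorded or drop out of the harms summary.** Section 9.1.1 exempts reporting, not recording. Side effects are monitored in both groups and collected at follow-up, and section 17 bases the CRF on the outcome measures.
- **That this is the only external safety signal.** The sponsor and REC have direct access to source data (section 13), and both receive a final report (section 14). These routes are slower, so the rule is the only *prompt* one.
- **That the protocol makes omission lawful.** Section 14 binds the trial to applicable regulations, and a protocol sentence cannot settle what those require.
- **That an injury caused by tiredness would be exempt.** This assumes miscoding. An injury is an event in its own right and is not among the listed symptoms.

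**Conclusion.** The point holds as a fault in the wording of the safety-reporting rule. The exception in the SAR/SUSAR sentence and the unrestricted list in 9.1.1 together allow a serious tiredness, nausea or headache reaction to go without immediate notice to the REC and sponsor. This rests on reading the two sentences literally and on 9.1.1 being the specification that the parenthesis refers to; the protocol contains no other.

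The size cannot be estimated. The exempt symptoms are the ones the protocol expects, and a reader might infer that the gap therefore covers the most likely serious reactions. That does not follow: nothing in the documents suggests that these symptoms are often serious. Expressing one supposed case as a share of an arm would show only scale, not how likely the case is.

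The protocol also does not say how serious events judged unrelated are handled. That is a separate matter and adds no weight here.

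**What to change.** Reconcile the Reporting Responsibilities sentence with section 9.1.1:

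- limit the 9.1.1 exemption to tiredness, nausea and headache that meet no seriousness criterion;
- delete *such as*, so that the list is closed;
- state that any reaction meeting a seriousness criterion is reported to the REC and sponsor, whatever its type;
- remove the parenthesis from the SAR/SUSAR sentence, or word it so that it cannot reach a serious reaction.

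This is a change of a few lines. It alters no treatment, endpoint, visit or sample size. The downside is possibly a few more reports.

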This section should contain all pertinent documents associated with the management of the study. The following lists a few examples of potential attachments:

- Patient Information Sheet
- Consent Form
